Full study protocol and statistical analysis plan

Official Title of the study:

Maternal plasma/urine/hair/amniotic fluid levels of selected trace elements and heavy metals in pregnancies complicated with neural tube defects

Date of the document:

August 2020.

Contents:

- 1. Participant Flow
- 2. Baseline Characteristics
- 3. Outcome Measures
- 4. Endpoints of the study
- 5. Limitations and Strengths
- 6. Certain Agreements
- 7. Results Point of Contact

1. Participant Flow

Recruitment Details

This observational case-control study will be conducted at the Department of Obstetrics and Gynecology, Cengiz Gokcek Public Hospital, Gaziantep, Turkey, between August 2020 and March 2021. The protocol was approved by the Ethics Committee for Clinical Research of Gaziantep University (reference no: 2020/167). The study strictly will be adhered to the principles of the Declaration of Helsinki. All subjects will be included in the study gave oral and written informed consent. 140 women were enrolled in the study in two groups.

Pre-assignment Details

The authors first will be assessed the recruited people to ensure meeting the inclusion and exclusion criteria. The inclusion criteria will be made according to the official documents.

Arm/Group Information *

There are two groups in the study.

Arm/Group Title *

Neural tube defect group

Control group

2. Baseline Characteristics

To detect significant difference between groups according to lead levels with a moderate effect size (Cohen's d =0.53), minimum required sample size was estimated as 45 for each group (α =0.05, 1- β =0.80). Power analysis was performed by using G power package version 3.1. Kolmogorov Smirnov and Shapiro Wilk tests will be used to test the normal distribution of data. For comparing groups (NTD/control) the student t-test will be used for variables that have a normal distribution, and the Mann Whitney U test will be used for variables that have not a normal distribution. The ROC analysis will be applied for the determination of cut-off point for variables. Moreover, Spearman correlation test will be used for the relationship of between variables. SPSS for Windows 22.0 and Medcalc programs will be used for statistical analysis. p<0.05 will be accepted as statistical significance.

3. Outcome Measures

Primary Outcome Measures: folic acid, zinc (Zn), molybdenum (Mo), vanadium (V), strontium (Sr), aluminum (Al), tin (Sn), antimony (Sb), mercury (Hg), calcium (Ca), iron (Fe), magnesium (Mg), phosphorus (P), barium (B) and selenium (Se) concentrations

Secondary Outcome Measures:

The elements and vitamins concentrations in the spinal NTD group and the cranial NTD group.

4. Endpoints of the study:

The primary outcome in these analyses will compare folic acid, zinc (Zn), molybdenum (Mo), vanadium (V), strontium (Sr), aluminum (Al), tin (Sn), antimony (Sb), mercury (Hg), calcium (Ca), iron (Fe), magnesium (Mg), phosphorus (P), barium (B) and selenium (Se) concentrations in NTD group and control group.

5. Limitations and strengths:

Our study has some strengths. These metals will be measured blood, urine and hair samples. So, these measurements may not reflect the metals exposure levels only recent exposure and will reflect before and during pregnancy.

6. Certain Agreements

This work will be supported by the Scientific Research Project Fund of Yozgat Bozok University.

7. Results Point of Contact

Corresponding Author: [name], Department of Obstetrics and Gynecology, Cengiz Gokcek Women's and Children's Hospital, Gaziantep, Turkey, [contact]

Address: [name]

GSM: [contact]

[contact]

[contact]

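### The only sample-size calculation is for lead, which is in neither primary outcome list, and its 45 per group matches 80% power for a one-sided t-test but gives 70% two-sided

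*Protocol*

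**What the plan says.** - **Sizing (Section 2, Baseline Characteristics).** The calculation is introduced with "To detect significant difference between groups according to lead levels with a moderate effect size (Cohen's d =0.53", and the result is that the "minimum required sample size was estimated as 45 for each group". Alpha is 0.05, power 0.80 and the software G*Power 3.1. No sidedness and no direction of effect are given. The significance threshold is a plain p<0.05.
- **Tests (Section 2).** Student's t-test is planned for normally distributed variables; otherwise "the Mann Whitney U test will be used for variables that have not a normal distribution".
- **Primary outcomes (Sections 3 and 4).** Section 3 opens its list with "Primary Outcome Measures: folic acid, zinc (Zn), molybdenum (Mo), vanadium (V), strontium (Sr), aluminum (Al), tin (Sn), antimony (Sb), mercury (Hg), calcium (Ca". Section 4 repeats the same 15 analytes and ends with "iron (Fe), magnesium (Mg), phosphorus (P), barium (B) and selenium (Se) concentrations in NTD group and control group". Lead is in neither list.
- **Secondary outcome (Section 3).** "The elements and vitamins concentrations in the spinal NTD group and the cranial NTD group". No individual element is named.
- **Enrolment (Section 1, Participant Flow).** "140 women were enrolled in the study in two groups". The split between the groups is not given.

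**The concern.** Two things in the sizing sentence do not fit the rest of the document.

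First, the variable that the study was sized on is not a listed outcome. The sizing sentence is the only place where lead is named. The title's reference to heavy metals and the secondary outcome's reference to elements could cover lead generically. However, the secondary outcome concerns spinal and cranial defects, whereas the calculation is for the defect and control groups. A reader cannot tell which endpoint the 80% belongs to.

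Second, a reader who sees an undirected difference and p<0.05 will take 45 per group as sufficient for an ordinary two-sided comparison. If it is not, any report that repeats the sentence will overstate what 45 per group can deliver.

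**Working it through.** **Inputs.** From Section 2: d = 0.53, alpha = 0.05, power = 0.80, two independent groups of equal size. From Section 1: 140 enrolled. Assumed, because the document does not give it: how the 140 divide.

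**Formula.** For a two-sample t-test with group sizes n1 and n2, df = n1 + n2 − 2 and the noncentrality is d × √(n1·n2/(n1 + n2)), which is d × √(n/2) for equal groups. Power is the probability that a noncentral t with these parameters exceeds the critical value (one-sided), or lies beyond it in either tail (two-sided).

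**Step 1: reproduce the plan's 45.** With 45 per group, the noncentrality is 0.53 × √22.5 = 2.514 and df = 88.

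| Test | n per group | Critical t | Power |
|---|---|---|---|
| One-sided | 44 | 1.663 | 79.4% |
| One-sided | 45 | 1.662 | 80.2% |
| Two-sided | 45 | 1.987 | 70.1% |
| Two-sided | 56 | 1.982 | 79.4% |
| Two-sided | 57 | 1.981 | 80.1% |

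The stated 45 is exactly the smallest one-sided size. The two-sided size is 57, which is 12 more per group.

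**Step 2: could rounding of d explain it?** If d = 0.53 is a rounded figure, it lies between 0.525 and 0.535. Two-sided, these limits need 58 and 56 per group. Rounding does not bring the two-sided answer near 45.

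**Step 3: what 45 per group detects two-sided.** Solving for 80% power at 45/45 gives d = 0.597, or about 0.60 against the stated 0.53.

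**Step 4: what the 140 enrolled give.** Two-sided t-test, d = 0.53, df = 138, critical t = 1.977:

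| Assumed split | Noncentrality | Power |
|---|---|---|
| 39/101 | 2.811 | 79.7% |
| 40/100 | 2.833 | 80.3% |
| 45/95 | 2.929 | 82.9% |
| 70/70 | 3.136 | 87.6% |

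Power is therefore at least 80% for every split with 40 or more in the smaller group. That includes every split that meets the protocol's own minimum of 45 in each group.

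**Step 5: is lead among the outcomes?** The list in Sections 3 and 4 is folic acid, zinc, molybdenum, vanadium, strontium, aluminum, tin, antimony, mercury, calcium, iron, magnesium, phosphorus, barium and selenium. That is 15 analytes, the same in both sections, without lead.

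**The case against.** **The study is large enough anyway.** This stands. The protocol calls 45 a minimum and reports 140 enrolled. A reader might infer from the 70% that the study is underpowered, but the documents do not support that. The 70% applies at 45/45, a total of 90, which is not the reported enrolment.

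**Sidedness is inferred, not stated.** This also stands. The document neither says that the calculation was one-sided nor rules it out. The match at exactly 45 makes a one-sided calculation the best explanation, and the undirected wording makes two-sided the natural reading, but neither is proof. Declaring a one-sided calculation openly, with its direction, would also repair the text.

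**The one-sided match is shown for the t-test only.** A reader might infer that 45 can arise in no other way under any planned test. The check does not show that. The protocol reserves Mann-Whitney for non-normal variables, and its sample size depends on the shape of the distribution: by relative efficiency, about 52 per group two-sided for logistic data and 38 for Laplace data. No standard option was found that gives exactly 45, but the exclusion is not complete.

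**The lead mismatch changes no number.** Correct as far as it goes. Cohen's d has no units, so the same n gives the same power for any single analyte with a true d of 0.53. But the protocol states that effect size for lead alone and for none of the 15 listed analytes. A reader might also infer that lead is not measured or was dropped. The generic wording in the title and the secondary outcome leaves that open.

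**Conclusion.** The point holds as an error in the sizing statement. The only stated power is attached to an analyte in neither primary list. The stated 45 per group delivers 80.2% one-sided but 70.1% two-sided by t-test, where 57 per group are needed for 80%. No shortfall in the study is shown.

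The figures rest on a single unadjusted t-test at alpha 0.05 with a true d of 0.53. The power figures for 140 further assume that all enrolled women are analysed, at the splits shown. The correction is worth making, but it is modest: it concerns what the study can say it was sized for.

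**What to change.** 1. **State lead's role in one sentence in Section 2.** Either it is a primary analyte (then add it to the lists in Sections 3 and 4), a secondary analyte, or a variable used for sizing only.
2. **State the sidedness.** Restate the calculation as two-sided for the t-test: either 57 per group for 80% power, or 45 per group with 70% power at d = 0.53 (detectable d about 0.60 at 80% power). Alternatively, declare that the calculation was one-sided, and in which direction.
3. **Give the actual split of the 140 and its two-sided power.** For orientation: 82.9% at 45/95 and 87.6% at 70/70 by t-test.

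The cost is wording in Section 2, and in Sections 3 and 4 only if lead is declared an outcome. No further enrolment or assay is called for, and naming lead as a sizing variable only adds no endpoint.

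### The minimum of 45 per group for lead matches a one-sided test that the protocol never declares; a two-sided t-test needs 57 per group

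*Protocol*

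**What the plan says.** The only sample-size justification is in Section 2 of the protocol, Baseline Characteristics. It sets the target as "To detect significant difference between groups according to lead levels with a moderate effect size (Cohen's d =0.53") and concludes that the "minimum required sample size was estimated as 45 for each group (α =0.05, 1- β =0.80"). G*Power 3.1 is named as the software. Whether the calculation was one-sided or two-sided is not said.

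The same section fixes the tests: "For comparing groups (NTD/control) the student t-test will be used for variables that have a normal distribution". Where normality fails, Mann-Whitney takes its place. The significance rule is "p<0.05 will be accepted as statistical significance", again with no side named.

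Section 1 (Participant Flow, Recruitment Details) adds that "140 women were enrolled in the study in two groups", without the number in each. Section 4 words the group comparison without direction for every listed analyte ("The primary outcome in these analyses will compare folic acid, zinc (Zn), molybdenum (Mo", and so on through the list).

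**The concern.** Effect size, alpha, power and equal allocation are all given, so the required number is determined once the sidedness is known. The aim is to find a difference, no direction is given for any analyte, and no one-sided test is declared. A reader will therefore take the calculation as two-sided at 0.05. On that reading, 45 per group is too few for the stated 80% power.

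What is at stake is the reliability of the protocol's one power statement. If the analysis is run two-sided, as the wording suggests, anyone relying on 45 per group as sufficient would have a noticeably weaker comparison than the protocol promises.

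**Working it through.** **Inputs.** All are from Section 2 of the protocol: d = 0.53 (standardised, so SD = 1), alpha = 0.05, power = 0.80, equal groups. The total of 140 is from Section 1. Its split is not stated, so every split below is an assumption.

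**Step 1. Normal approximation.** n per group = 2(z_alpha + z_power)² / d², with d² = 0.2809 and z_power = 0.8416.
- One-sided: 2(1.6449 + 0.8416)² / 0.2809 = 44.02, rounded up to 45.
- Two-sided: 2(1.9600 + 0.8416)² / 0.2809 = 55.88, rounded up to 56.

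**Step 2. Exact t-test.** Power comes from the noncentral t distribution with df = 2n − 2 and noncentrality d√(n/2).

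| n per group | Sides | Noncentrality | Critical t | Power |
|---|---|---|---|---|
| 45 | one | 0.53 × √22.5 = 2.514 | 1.662 | 0.802 |
| 45 | two | 2.514 | 1.987 | 0.701 |
| 56 | two | 0.53 × √28 = 2.804 | 1.982 | 0.794 |
| 57 | two | 0.53 × √28.5 = 2.829 | 1.981 | 0.801 |

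Solving for 80% power gives n = 44.71 (45) one-sided and n = 56.86 (57) two-sided. The plan's 45 is thus reproduced exactly by the one-sided test. Against 57, the shortfall is (57 − 45) / 57 = 21%.

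**Step 3. Can something else explain 45 in a two-sided test?**
- *Rounding of d.* From 0.525 to 0.535, the two-sided t-test needs 58 down to 56 per group.
- *A different alpha.* With 45 per group, 80% two-sided power requires alpha of about 0.098, not 0.05.
- *A different effect.* With 45 per group, the effect detectable with 80% two-sided power is d = 0.597, not 0.53.
- *Mann-Whitney.* Dividing 56.86 by the asymptotic relative efficiency gives the two-sided requirement:

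| Distribution | Efficiency | n per group |
|---|---|---|
| Laplace | 1.5 | 37.91 (38) |
| Logistic | π²/9 | 51.85 (52) |
| Uniform | 1 | 56.86 (57) |
| Normal | 3/π | 59.54 (60) |
| Least efficient case | 0.864 | 65.81 (66) |

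None of these is 45. One-sided Mann-Whitney with a uniform distribution does give 45, because its efficiency is 1.

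**Step 4. What the 140 women provide, two-sided at d = 0.53.** For unequal groups the noncentrality is d√(n₁n₂/(n₁ + n₂)).

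| Assumed split | t-test | Mann-Whitney, normal data | Mann-Whitney, least efficient case |
|---|---|---|---|
| 70/70 | 0.876 | 0.860 | 0.824 |
| 45/95 | 0.829 | 0.811 | 0.770 |

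For the t-test, 40/100 gives 0.803 and 39/101 gives 0.797, so 80% holds if the smaller group has at least 40. The corresponding thresholds are 43 for Mann-Whitney with normal data (0.801; 42 gives 0.796) and 53 in the least efficient case (0.801; 52 gives 0.798).

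A simulation of two-sided Mann-Whitney on normal data (40,000 runs) agrees with the efficiency method: 0.680 at 45/45, 0.804 at 60/60, 0.864 at 70/70 and 0.810 at 45/95.

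**The case against.** The strongest reply is that 45 is correctly computed: a one-sided t-test gives exactly that number. This is true, and it means the fault is an undeclared one-sided basis rather than a slip in the sums. It does not rescue the sentence, because a one-sided test has to be declared and given a direction, and the protocol does neither.

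The two-sided reading is an inference. The wording in Section 2 is generic, and the list in Section 4 does not include lead, so it is only indirect evidence about the lead comparison. A directional expectation for a toxic metal is conceivable. That point stands, and it is why the 21% shortfall is conditional on the two-sided reading.

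A two-sided Mann-Whitney test could also return 45 for some distribution with relative efficiency of about 1.26 (56.86 / 45), between the logistic and Laplace cases. The protocol names no such distribution, and the one-sided t-test is by far the likelier source.

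Finally, 140 women exceed both 2 × 45 = 90 and 2 × 57 = 114, so the practical effect may be nil. This limits the weight of the point but does not remove it. The split is not given, and the stated minimum still misreports what 80% two-sided power requires.

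**Conclusion.** The concern holds. With the stated inputs, 45 per group is the one-sided answer; the two-sided t-test at 0.05 needs 57. On the two-sided reading, which fits the undirected aim, the stated minimum is about 21% too low and carries about 70% power instead of 80%.

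The fault lies in the stated minimum. It is not evidence of an underpowered study, since the 140 women give at least 80% two-sided t-test power as long as the smaller group has at least 40. The conclusion assumes a two-sided test and takes d = 0.53 as given. The figures for the 140 women also depend on the assumed splits. The point should be corrected, but it does not threaten the design.

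**What to change.** In Section 2, state that the test is two-sided and that d = 0.53, alpha = 0.05 and 80% power require 57 per group for the t-test, in place of 45. If the past calculation is to stay on record, label it as one-sided and give 57 beside it. If a one-sided lead test was really intended, it must be declared and justified.

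State how the 140 women divide between the groups and give the two-sided power for that split (about 88% if 70/70, about 83% if 45/95). Add that 57 applies to the t-test and that the Mann-Whitney requirement depends on the distribution, at about 60 per group if the data are normal.

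The cost is wording and a less favourable stated minimum. At 70/70, no added enrolment is needed under the t-test or under Mann-Whitney, even in its least efficient case. For a less balanced split this depends on the thresholds of 40, 43 and 53 given above. At 45/95, for example, the least efficient Mann-Whitney case falls to 0.770, and the smaller group is below 57 although t-test power stays above 80%.

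Lead is also absent from the outcome lists in Sections 3 and 4. That is a separate mismatch, which this correction does not settle.

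### The pooled-variance Student t-test is fixed without a variance condition or a stated group split, so its type I error can miss 5% if group sizes and SDs both differ; Welch's test avoids this

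*Protocol*

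**What the plan says.** The statistical methods stand in section 2 (Baseline Characteristics) of the Protocol. The route to the test is a normality check: "Kolmogorov Smirnov and Shapiro Wilk tests will be used to test the normal distribution of data". For variables that pass, "the student t-test will be used for variables that have a normal distribution"; for the rest, "the Mann Whitney U test will be used for variables that have not a normal distribution". The significance rule is "p<0.05 will be accepted as statistical significance", with sidedness not given. No unequal-variance version of the t-test and no check of the variances is named.

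On group sizes, section 2 states that the "minimum required sample size was estimated as 45 for each group", and section 1 (Participant Flow) that "140 women were enrolled in the study in two groups". The division of the 140 between the NTD and control groups is not stated. The rule applies to the primary comparison in section 4, which covers 15 analytes. The document's title presents it as protocol and analysis plan together, so the test is a choice made here and not one left open.

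**The concern.** The pooled-variance t-test estimates one common SD. If the SDs differ and the groups are of equal size, the error in the standard error cancels. If the groups are unequal, it does not cancel. The test is then too liberal when the smaller group is the more variable one, and too conservative when the larger group is. Passing a normality test gives no protection, because normal data with unequal SDs go straight to the t-test.

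At stake is the false-positive rate of the primary comparison for analytes judged normal or, in the opposite direction, the chance of missing a real difference.

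**Working it through.** **Inputs from the Protocol.** Total 140; minimum 45 per group; d = 0.53; alpha 0.05; power 0.80.

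**Assumptions.** Splits of 140 from 70/70 to 45/95, where 95 = 140 - 45 is the most uneven split that still meets the stated minimum. SD ratios (smaller group / larger group) from 0.5 to 2. Two-sided tests at 5%.

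**The plan's own figure.** n per group = 2(z_alpha + z_beta)² / d².
- One-sided: 2 × (1.645 + 0.842)² / 0.53² = 44.0, rounded up to 45. The exact t calculation gives 44.7, so 45.
- Two-sided: 2 × (1.960 + 0.842)² / 0.53² = 55.9, so 56. The exact t calculation gives 56.9, so 57.

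The stated 45 is therefore reproduced as a one-sided figure. That is a separate matter; here 45 serves only as the smallest group size the text supports.

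**Type I error of the pooled test, large-sample formula.** With group sizes n1, n2 and SDs s1, s2:
- pooled variance sp² = [(n1 - 1)s1² + (n2 - 1)s2²] / (n1 + n2 - 2)
- variance the test uses: Vp = sp²(1/n1 + 1/n2)
- true variance: V = s1²/n1 + s2²/n2
- type I error = 2[1 - Φ(1.96 √(Vp/V))]

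Example, 45/95 with the smaller group's SD twice as large: sp² = (44 × 4 + 94) / 138 = 1.957; Vp = 1.957 × 0.03275 = 0.0641; V = 4/45 + 1/95 = 0.0994; √(Vp/V) = 0.803; 1.96 × 0.803 = 1.57; error = 11.6%.

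At 70/70, Vp = V whatever the SDs, so the error is 5%.

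| Split (smaller/larger) | ratio 0.5 | 0.67 | 1 | 1.5 | 2 |
|---|---|---|---|---|---|
| 70/70 | 5.0% | 5.0% | 5.0% | 5.0% | 5.0% |
| 60/80 | 3.3% | 3.8% | 5.0% | 6.4% | 7.2% |
| 50/90 | 2.0% | 2.9% | 5.0% | 8.0% | 10.0% |
| 45/95 | 1.5% | 2.5% | 5.0% | 8.8% | 11.6% |

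**Simulation of the t-tests** (20,000 normal replicates per setting). Student at 45/95: 9.0% and 11.8% at ratios 1.5 and 2, and 2.5% and 1.5% when the larger group's SD is 1.5 and 2 times larger. Student at 60/80: 6.4% and 7.3% at ratios 1.5 and 2. Welch stays at about 5% throughout.

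**Simulation of the whole rule** (8,000 normal replicates; Shapiro-Wilk in each group, then Student or Mann-Whitney). About 90% of samples pass to the t-test.

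| 45/95, SD ratio | rule as written | same rule with Welch | Welch always |
|---|---|---|---|
| 0.5 | 1.8% | 4.7% | 4.8% |
| 1.5 | 8.7% | 5.2% | 4.7% |
| 2 | 11.7% | 5.9% | 5.1% |

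The small excess at ratio 2 with Welch in the rule comes from the samples still sent to Mann-Whitney, which alone rejects 8.9% there. At 70/70 the rule as written gives 4.8% to 5.9% over SD ratios 0.5 to 2.

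**Is the pre-test a source of error?** With identical distributions in both groups (normal, or lognormal with log-SD 0.25 or 0.5), the rule as written gives 4.6% to 5.5% at 70/70 and 45/95.

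**Cost of Welch under equal variances** (d = 0.53, 8,000 replicates). At 45/95 power goes from 0.828 to 0.821, a loss of 0.7 points. At 70/70 there is no loss.

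**The case against.** The strongest reply is that the high error rates need three things at once: normal data, a clearly uneven split and unequal SDs. The document states no split and no SDs, and the 45 per group is an equal-group power figure. A reader might infer that 45/95 is planned; nothing says so, and at 70/70 the problem disappears. Skewed analytes also mostly leave the t-test: with lognormal data at 70/70 and log-SD 0.35, both normality tests pass in only 2% of samples. All of this stands. It makes the point conditional and limits it to analytes that pass the normality check. It does not remove it, because the split is open and the test is fixed regardless.

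A reader might also infer that choosing the test from two normality tests, with no rule for when they disagree, inflates the error. They do disagree in 22-39% of lognormal samples at 70/70 with log-SD 0.25-0.35, though in only 4% at 0.5 and almost never at 0.8. Yet taking the smaller p-value at every disagreement, with identical groups and log-SD 0.25-0.8, gave only 4.3-5.1% at 70/70 and 5.0-5.6% at 45/95. The inflation is therefore not shown.

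Nor do the documents support the view that all analytes must go on one log scale. Section 4 asks only for an NTD-control comparison of each concentration, with no ranking or pooling across analytes. A log-scale Welch test also changes the target to geometric means. With equal arithmetic means and log-SDs of 0.8 and 0.5 at 70/70 it rejects 40% of the time, much as Mann-Whitney does (38-40%). Its power was 0.87-0.88 against 0.86 for the planned rule, a slight gain.

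**Conclusion.** The point holds conditionally and is minor. Student's test is fixed with no variance condition while the group split is unstated. At 70/70 its type I error is about 5%. With unequal groups and a smaller group whose SD is 1.5-2 times larger, it is about 6-7% at 60/80 and 9-12% at 45/95. With the larger SD in the larger group it falls to 1.5-2.5% at 45/95. The splits and SD ratios are assumptions, 45/95 is the extreme case, and reading Student's test as the pooled-variance test is the ordinary usage, not a word of the document. The departure from 5% comes from pooling the variances in unequal groups, and not from the normality pre-test.

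**What to change.** In section 2, replace the Student t-test by the Welch (unequal-variance) t-test for variables judged normal. The rest of the rule can stay. This changes one term, uses software already named, and costs less than 1 point of power if the variances are equal. Stating the NTD:control split in section 1 would help the reader judge how much the choice matters, but Welch's test does not depend on it. Analysing every analyte on the log scale with geometric mean ratios is optional and not part of this fix.

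### Fifteen analytes are all primary and the only rule is an unadjusted p<0.05, so a false-positive primary finding is likely even if nothing differs

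*Protocol*

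**What the plan says.** The document is headed "Full study protocol and statistical analysis plan" and refers to no other plan for its analysis rules.

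- **Primary outcomes (section 3).** The list begins "Primary Outcome Measures: folic acid, zinc (Zn), molybdenum (Mo), vanadium (V), strontium (Sr" and continues with aluminum, tin, antimony, mercury, calcium, iron, magnesium, phosphorus, barium and selenium: 5 + 10 = 15 analytes.
- **Endpoints (section 4).** The same 15 are named again as what the primary analysis compares between the NTD and control groups.
- **Tests (section 2).** "For comparing groups (NTD/control) the student t-test will be used for variables that have a normal distribution"; otherwise a Mann-Whitney test is used.
- **Decision rule (section 2).** "p<0.05 will be accepted as statistical significance". Sidedness is not given.
- **Sample size (section 2).** The calculation starts "To detect significant difference between groups according to lead levels with a moderate effect size" (d = 0.53, α = 0.05, power 0.80) and concludes that "minimum required sample size was estimated as 45 for each group". Lead is not among the 15 primary analytes.
- **Enrolment (section 1).** "140 women were enrolled in the study in two groups"; the split is not given.
- **Specimens.** The official title lists plasma, urine, hair and amniotic fluid. Section 5 lists blood, urine and hair. Sections 3 and 4 do not say which specimen the primary comparisons use.

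**The concern.** A primary outcome is the result on which a study is judged. Here 15 results share that status and each is judged alone at 5%. Nothing says which analyte leads, how many must differ, or how one positive among 15 should be read.

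A report could therefore present whichever analyte crosses the threshold as a significant primary finding and be fully within the plan. An isolated p just under 0.05 would be weak evidence that the analyte is associated with neural tube defects, yet the stated rule gives it the same standing as a single pre-named primary result.

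This is more than a detail left to a later plan. The document sets an unqualified threshold for variables that it calls primary.

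**Working it through.** **1. The protocol's own figure.** Inputs from section 2: d = 0.53, α = 0.05, power 0.80, equal groups. Power comes from the noncentral t distribution with 2n − 2 degrees of freedom and noncentrality d√(n/2). For n = 45 the noncentrality is 0.53 × √22.5 = 2.51.

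- One-sided: power 0.802, and 45 is the smallest n reaching 0.80. The stated figure is reproduced.
- Two-sided: power 0.701; 57 per group would be needed.

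So the stated 45 fits a one-sided test only. Because the protocol does not give sidedness, both cases are shown below.

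**2. Expected false positives if nothing differs.** 15 × 0.05 = 0.75, whatever the correlation.

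**3. Chance of at least one p<0.05 among the 15 if nothing differs.** With uncorrelated tests this is 1 − 0.95^15 = 0.537. With a common positive correlation ρ, and c = 1.96 for two-sided tests, it is

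1 − ∫ φ(u) [Φ((c − √ρ·u)/√(1−ρ)) − Φ((−c − √ρ·u)/√(1−ρ))]^15 du.

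For one-sided tests c = 1.645 and the second Φ term is dropped. The analytes come from the same women, so some correlation is likely. The document gives none, so ρ is assumed.

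| ρ (assumed) | Two-sided | One-sided |
|---|---|---|
| 0 | 0.537 | 0.537 |
| 0.3 | 0.457 | 0.386 |
| 0.5 | 0.361 | 0.300 |
| 0.7 | 0.256 | 0.217 |
| 0.9 | 0.144 | 0.128 |

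A simulation of the two-sided case with 400,000 draws gave 0.536, 0.361 and 0.144 at ρ = 0, 0.5 and 0.9. Relative to 5%, the two-sided figures run from 0.144/0.05 = 2.9 times to 0.537/0.05 = 10.7 times. The value at 0.9 is not a floor: higher correlation would bring it closer to 5%.

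**4. What adjustment would cost.** Holm's first step tests at 0.05/15 = 0.0033. The figures below are two-sided and use d = 0.53 only as an illustration, since the protocol gives it for lead. The 70/70 split of the 140 women is assumed.

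| | 70/70 | 45/45 |
|---|---|---|
| Power at 0.05 | 0.876 | 0.701 |
| Power at 0.05/15 | 0.560 | 0.315 |
| d detectable with 80% power at 0.05 | 0.48 | 0.60 |
| d detectable with 80% power at 0.05/15 | 0.65 | 0.82 |

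Keeping 80% power at 0.05/15 needs 104 per group.

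Benjamini-Hochberg at 5% was simulated with 1, 3 or 5 true differences of d = 0.53 among the 15:

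| | Power (1 / 3 / 5) | Chance of any false positive (1 / 3 / 5) |
|---|---|---|
| 70/70, ρ = 0 | 0.570 / 0.670 / 0.733 | 0.076 / 0.121 / 0.148 |
| 70/70, ρ = 0.5 | 0.563 / 0.658 / 0.713 | 0.057 / 0.081 / 0.097 |
| 45/45, ρ = 0 | 0.322 / 0.390 / 0.447 | 0.064 / 0.091 / 0.111 |
| 45/45, ρ = 0.5 | 0.317 / 0.392 / 0.445 | 0.054 / 0.071 / 0.082 |

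All power figures assume normal data and t-tests. They do not cover analytes that go to the Mann-Whitney test.

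**The case against.** The strongest reply is that this is an observational case-control study that promises no family-wise error rate. Each test keeps its nominal 5%, and nothing says that one significant analyte makes the study positive. Whether to adjust across many analytes in an association study is disputed, and reporting all 15 unadjusted can be defended. That stands as far as it goes, and it is why relabelling without adjustment is among the acceptable fixes. But the protocol does not call the work exploratory. It names primary outcomes and gives a sample size at a stated α and power, so a reader will take a primary p<0.05 as confirmatory.

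A second reply is that the 54% assumes every analyte is null and all tests are uncorrelated, and that for two-sided normal tests this is the maximum. That is right, and the range should be read as a whole. The firm figure is 0.75 expected false positives if nothing differs. Even at a correlation of 0.9 the chance of at least one is nearly three times 5%.

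A third is that sidedness, the lead-based sample size and the specimen mismatch are separate faults. They are, and they add nothing to the size of this one. They matter here because a multiplicity rule cannot be written until the tests and the family are defined.

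A separate analysis plan might hold a rule, but this document describes itself as that plan and defers nothing.

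**Conclusion.** The concern holds and should be fixed. Fifteen analytes carry equal primary status under an unqualified p<0.05. If none differs, 0.75 false-positive primary results are expected. The chance of at least one is 54%, 36% or 14% at correlations of 0, 0.5 and 0.9 (two-sided), or 54%, 30% or 13% (one-sided).

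These figures assume one test per analyte and one common positive correlation. No figure is given for several specimens, because the protocol does not say which analytes are measured in which. If the family is the 15 analytes in one specimen, a p below 0.0033 would survive correction; a larger family would need a smaller one.

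No single test is invalid and no stated error claim is broken. What is at stake is how far one significant primary result can be believed.

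**What to change.** 1. **State that the tests are two-sided**, and give the sidedness of the sample-size calculation. The stated 45 per group has power 0.80 only one-sided and 0.70 two-sided.
2. **Replace the bare threshold for the 15 primary comparisons** with one of these, fixed before analysis:
   - (a) Holm-adjusted p<0.05, which controls the family-wise error.
   - (b) Benjamini-Hochberg at 5%, stating that it controls the false discovery rate and not the family-wise error, and that this relies on independence or suitable positive dependence among the tests.
   - (c) One named primary analyte at two-sided 0.05 with its own effect-size basis, since d = 0.53 is for lead. The other 14 become secondary, with a statement that they carry no confirmatory claim.
   - (d) All 15 labelled exploratory, with every estimate and confidence interval reported and no confirmatory claim.
3. **State which specimen or specimens the primary family covers**, reconciling the title with section 5. If more than one is primary, apply the chosen adjustment across all analyte-specimen comparisons.

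The cost is wording and a simple calculation, with no new data, but (a) and (b) have a real price in power. At d = 0.53, Holm's first step takes it from 0.88 to 0.56 at 70/70 and from 0.70 to 0.31 at 45/45. Benjamini-Hochberg gives about 0.56 to 0.73 at 70/70 and 0.32 to 0.45 at 45/45. Adjusting across several specimens would cost more. Option (d) costs no power but gives up any confirmatory claim.
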